### III. Statistical design

- a. Sample size: Two sequential cohorts of 12 residents living in a HUD subsidized independent-living senior housing community in Ypsilanti, MI will be recruited for participation in this study. Both cohorts will receive the same intervention. The size of each cohort is capped at 12 to facilitate participation among all participants during group components of the intervention. A sample size of 24 was estimated to be sufficient in order to reach data saturation from quantitative process measures and theoretical saturation of themes from qualitative (i.e., open-ended) evaluation data (see Aim #2 below).
- b. AIM 1) Identify agents of change (AoC) and implement intervention. Within two sequential cohorts of 12 residents living in a HUD subsidized independent-living senior housing community, AoC will be identified.
  - i. Data analysis plan: Within each group of 12 study participants AoC will be identified using data collected during the pre-intervention interview. Specifically, during the interview, study participants will be asked to identify people they know in the community. Next, social network analysis will be conducted using these data with Ucinet. AoC will be identified as the top two study participants in their cohort on the social network measure of in-degree centrality (i.e., number of other study participants who report knowing them).
  - ii. Power analysis: A power analysis was not conducted for the proposed analysis due to the descriptive nature of the social network analyses.

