- c. AIM 2) Evaluate feasibility of intervention implementation. Process outcomes will be examined following intervention implementation to determine which components were feasible. The process evaluation will be guided by a framework for evaluating complex interventions that assesses implementation, mechanisms of impact, and context. Process measures will include: 1) number of original AoC who accept invitation to serve on the Advisory Committee; 2) number of committee meetings attended by AoC; 3) number of individual (one-on-one) activities attended by study participants; 4) number of group activities attended by study participants; 5) total number of intervention activities attended by study participants; and 6) number of remote activities that study participants attended via zoom. Hypotheses: The following process hypotheses will be tested H2a: At least 75% (3 of 4) of identified AoCs will accept the invitation to serve on Advisory Committee; H2b: AoC will attend at least 2 of 3 committee meetings; H2c: Participants will on average participate in at least 70% (7 of 10) of intervention activities.
  - i. Data analysis plan:
    1. Quantitative analysis: Descriptive analysis of process outcomes and intervention usefulness/satisfaction data from post-intervention interviews will be conducted using statistical software (e.g. SPSS). This will include examination of variable frequencies, measures of central tendency, and sample variation.
    2. Qualitative analysis: Analysis of open-ended data from questions about the usefulness and satisfaction with specific intervention

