- e. For those screened to participate on-site, this informed consent process will occur directly after the screening interview. At the time of the in-person visit, the study team member will go over the consent form with the participant and answer any questions the participant may have. The participant will then be asked to print their name, sign and date the informed consent document. The signed copy will be taken and kept with study records and the participant will be given an unsigned copy for keep for their records. Following this, the time and date for the participant's pre-program interview will be confirmed.
- f. Consent will be collected a third time for only specific participants, the study's identified agents of change (AoC) for their role in the intervention as a member of the intervention's Advisory Committee. Two AoC per cohort will be recruited over the telephone. If they are interested in the role, consent to take on the role will be obtained in-person when visiting the participant to pick up their activity monitor.
- g. At the time of the in-person visit, the study team member will go over the consent form with the participant and answer any questions the participant may have about the role. The participant will then be asked to print their name, sign and date the informed consent document. The signed copy will be taken and kept with study records and the participant will be given an unsigned copy for keep for their records. All study informed consent documents will contain a statement informing participants that results from this study will be posted online at ClinicalTrials.gov.

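### The plan says 24 participants suffice for data saturation of quantitative process measures, but counts and means do not saturate and no precision criterion is given

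*Combined protocol and SAP*

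**What the plan says.** Section III.a plans two cohorts of 12. It gives a practical reason for the cohort size: "The size of each cohort is capped at 12 to facilitate participation among all participants during group components of the intervention". It then makes one statement about the adequacy of the total: "A sample size of 24 was estimated to be sufficient in order to reach data saturation from quantitative process measures". The same sentence goes on to claim "theoretical saturation of themes from qualitative (i.e., open-ended) evaluation data (see Aim #2 below", which ties both halves to Aim 2.

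Section III.c (Aim 2) lists the process measures. All are numbers: agents of change (AoC) who accept, committee meetings attended, and individual, group, total and remote activities attended. Hypotheses on these measures are to be tested, among them "H2a: At least 75% (3 of 4) of identified AoCs will accept the invitation to serve on Advisory Committee" and, as H2c, "Participants will on average participate in at least 70% (7 of 10) of intervention activities". The quantitative analysis is descriptive: frequencies, central tendency and variation, with no interval.

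The power paragraph under Aim 2 says that no power analysis was done because the analyses are descriptive. Section III.g says the same for the pilot as a whole, because the sample is small and not representative. Section III.f plans 95% confidence intervals, but only for the Aim 3 comparison of participants who did and did not know an AoC at baseline.

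**The concern.** The qualitative half of the sentence uses saturation in its usual sense: collection is sufficient when more respondents stop yielding new themes. The quantitative half has no such meaning. A count or mean has a standard error that shrinks with the number of participants, and at no sample size does it become complete. To call 24 sufficient for these measures one needs a criterion, such as an interval width, and none is stated.

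What is at stake is how the feasibility results are read. Aim 2 is meant to show which components were feasible, and its benchmarks are framed as hypotheses. With no interval planned, a bare point estimate at or just above 7 of 10, or 3 of 4, would count as a pass. The sufficiency statement could then be taken as support for that reading.

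**Working it through.** **Inputs from the documents**
- Total: 2 × 12 = 24 (section III.a).
- AoC: "Two AoC per cohort will be recruited over the telephone" (section VI.f), so 2 × 2 = 4, the denominator of H2a.
- Activities per participant: 1 initial one-on-one + 4 group sessions + 4 brief check-ins + 1 final one-on-one = 10 (section II.u to II.x), the denominator of H2c.
- Confidence level: 95%, borrowed from section III.f.

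**Inputs assumed**
- SD of activities attended: the plan gives none. The main range is 2 to 3, the wider range 1.5 to 3.5.
- Dropout: no rate is given; 18 participants with data is used as a low case.
- Within-cohort correlation: none is given; an ICC of 0.05 is used for illustration.

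**The plan's own figure.** The products 24, 4 and 10 agree with the text, as do 3/4 = 75% and 7/10 = 70%. The sufficiency of 24 cannot be reproduced, because the plan states no precision target, SD, effect size or saturation criterion for the process measures.

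**H2c: 95% half-width = t(0.975, n−1) × SD/√n.** With n = 24, t = 2.069 and √24 = 4.899.

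| Assumed SD | Half-width | Observed mean at which the lower limit reaches 7 | P(observed mean ≥ 7) if the true mean is 6.5 |
|---|---|---|---|
| 2.0 | 0.84 | 7.84 | 0.11 |
| 2.5 | 1.06 | 8.06 | 0.16 |
| 3.0 | 1.27 | 8.27 | 0.21 |

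The last column is 1 − Φ(0.5/(SD/√24)), a normal approximation. Over SD 1.5 to 3.5 the half-width runs from 0.63 to 1.48.

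Two things would widen these intervals:
- *Dropout.* With n = 18, the half-width at SD 2, 2.5 and 3 is 0.99, 1.24 and 1.49.
- *Shared group sessions.* Participants in a cohort share sessions and a committee, and the amendment note in sections II and III places the second cohort in a different community. At an ICC of 0.05 the design effect is 1 + 11 × 0.05 = 1.55. Since √1.55 = 1.245, the interval is about 24% wider.

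**H2a: exact (Clopper-Pearson) interval, n = 4**
- 3 of 4, lower limit: solve 4p³(1−p) + p⁴ = 0.025, giving p = 0.194.
- 3 of 4, upper limit: solve 1 − p⁴ = 0.025, giving p = 0.994. The interval is 19% to 99%.
- 4 of 4, lower limit: 0.025^(1/4) = 0.398, so even full acceptance is compatible with a true rate of 40%.
- Chance of at least 3 of 4 when the true rate is 50%: (4 + 1)/16 = 0.31. When the true rate is 75% it is 0.74.

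**The case against.** The case on the other side is substantial.

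- *The sample-size sentence does not mention H2a to H2c.* A reader might infer that the plan declares 24 adequate to establish the 70% and 75% thresholds. It does not. It speaks of process measures and points to Aim 2, and the step to the thresholds is the reader's own. This stands.
- *No power analysis is claimed.* Sections III.c and III.g say so openly, and III.g warns that such a sample is likely to give inaccurate estimates. It would be wrong to infer that the plan hides the lack of a statistical basis. This stands, but disclaiming power does not support a separate, positive claim of sufficiency.
- *Saturation is not the only rationale.* The cap for group delivery and the saturation of themes in the open-ended data are both legitimate. A reader might go further and say that the cap is the real source of 24. The documents support only part of that: the cap explains 12 per cohort, not why there are two cohorts.
- *H2a rests on four people however the sentence about 24 is worded.* This stands. Its interval belongs here only because H2a is one of the process benchmarks that would be reported without one.
- *The thresholds may be benchmarks for the observed sample.* That is a fair reading for a single-arm pilot with a descriptive analysis. But the plan calls them hypotheses to be tested and does not say which reading applies, so the report should.
- *The H2c figures rest on assumed SDs and independence.* This stands, so they must be labelled illustrative and not written in as properties of the design.

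**Conclusion.** Section III.a claims an adequacy for quantitative measures that the design does not have and that no calculation supports. The claim should go. The related gap is that Aim 2 sets numerical benchmarks without intervals, while Aim 3 has them.

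For H2c the illustrative half-width is about 0.8 to 1.3 activities out of 10, given an SD of 2 to 3 and 24 independent participants with data; dropout or within-cohort correlation makes it wider. For H2a, an observed 3 of 4 is compatible with 19% to 99%. Neither result, at or just above its threshold, establishes that the underlying rate or mean reaches it.

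A reader might infer that the trial is too small or needs a power calculation. The documents do not support that: this is a feasibility pilot with a descriptive analysis, and the lack of a power analysis is disclosed. Severity is minor.

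**What to change.** 1. **Section III.a.** Delete the claim of saturation for quantitative process measures and keep it for the open-ended data. State that cohorts are capped at 12 for group delivery and that 24 was not chosen for statistical precision.
2. **Section III.c (Aim 2).** Report H2a, with its denominator of 4, and H2c with 95% intervals, as already planned for Aim 3.
3. **Wording of results.** Describe a threshold as met in the observed sample, not as established, unless the interval excludes values below it. For H2a no result can reach that standard, because 4 of 4 has a lower limit of 40%.
4. **If precision figures are added,** label them illustrative and give their assumptions: for H2c about ±0.8 to 1.3 activities at SD 2 to 3 with 24 independent participants, wider with dropout or within-cohort correlation; for H2a 19% to 99% at 3 of 4.

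The cost is a few sentences, a little more reporting and a less favourable justification of the sample size. Recruitment, sample size and intervention do not change.

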- e. Analysis of accelerometry data: This study will use an accelerometer (activPAL) to measure physical activity among study participants. The activPAL is worn on the thigh continuously for 7-days. It has been shown to reliably measure sedentary time (including lying and sitting time) and activity intensity (i.e., estimates of energy expenditure) (Lyden et al., 2018). Raw data from the activPAL will be exported using activPAL provided software to a .csv file. The data will then be processed using an R-

package developed by developed specifically for activPAL data (Lyden et al, 2018). The data will be processed at the second level (1-second epochs). The same R-package will then be used to sum the following over the 7-day period I which the device was worn: 1) sedentary (i.e. sitting/lying) time (i.e., number of 1-second epochs of <1.50 metabolic equivalents); 2) light activity (i.e., standing and stepping) time (i.e., number of 1-second epochs between 1.50 and 2.99); and 3) moderate or higher activity time (i.e., number of 1-second epochs 3.00 or higher). The above data preparation and analysis steps will be applied to both the pre- and post-intervention accelerometry data. As a final step we will create changes scores in each of the three objectively measured indicators of activity (sedentary, light, and moderate or higher). Following creation of these variables, descriptive analysis will be conducted on these variable including examination of frequencies, measures of central tendency, and sample variation.

- f. Hypothesis testing: To test the proposed hypotheses (i.e., to test the presence of social network influence), mean differences and corresponding 95% confidence intervals in process measures (e.g., number of intervention activities that study participants participated in) and changes in secondary outcomes described above will be compared between study participants who knew one or more AoC at baseline and those who did not. Next, within these two groups we will stratify by pain measures to explore descriptively whether pain moderates network influence on outcomes.
- g. Power analysis: A power analysis was not conducted for this pilot study given the proposed small non-representative sample, which is likely to produce inaccurate estimates of effect size and their corresponding standard errors.

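### H2a to H2c are announced as tested hypotheses, but the Aim 2 analysis is descriptive with no interval or test; label them benchmarks and give the H2c mean a 95% CI (minor)

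*Combined protocol and SAP*

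**What the plan says.** Section I.b.ii (Specific Aims) and Section III.c (Aim 2) both present the process hypotheses as ones to be tested. III.c puts it this way: "The following process hypotheses will be tested H2a: At least 75% (3 of 4) of identified AoCs will accept the invitation". The H2a criterion is thus three acceptances among four people. H2b asks for AoC attendance at two or more of the three meetings of the committee. H2c sets a benchmark for mean participation: "Participants will on average participate in at least 70% (7 of 10) of intervention activities".

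The process measure behind H2a is the "number of original AoC who accept invitation to serve on the Advisory Committee", so a replacement recruited after a refusal does not count. III.c adds that the process outcomes are examined in order to establish which components were feasible.

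The quantitative analysis for Aim 2 (III.c.i.1) is descriptive: "This will include examination of variable frequencies, measures of central tendency, and sample variation". The Aim 2 power paragraph repeats that the analysis is descriptive. No test, interval or rule for results near a threshold is given.

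III.f (Hypothesis testing) plans "mean differences and corresponding 95% confidence intervals", but only for comparing participants who knew at least one AoC at baseline with those who knew none. The paragraph defines its own scope as testing for social network influence, which is Aim 3.

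**The concern.** A hypothesis that is tested has some link between the data and a statement about the underlying rate or mean. Here there is none: the analysis yields an observed count or mean, and all that can be said is whether it reached the stated number. Feasibility is the stated objective of this pilot (Section I.a), yet the acceptance proportion, AoC attendance and mean participation have no interval, while the network contrast in III.f does. If the wording stays, a met threshold can be written up as a supported hypothesis on data that are also compatible with values well below the threshold.

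**Working it through.** **1. The plan's own figures.** Two AoCs per cohort ("AoC will be identified as the top two study participants in their cohort") in 2 cohorts gives 4, and 3/4 = 75%. Activities per Sections II.u to II.x: 1 initial individual meeting + 4 group sessions + 4 weekly check-ins + 1 final individual meeting = 10, and 7/10 = 70%. Sample: 2 × 12 = 24. All three agree with the text. The 24 is justified by saturation, so there is no precision figure to reproduce.

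**2. H2a, X ~ Binomial(4, p), criterion X ≥ 3.**
- p = 0.50: P(X ≥ 3) = 4(0.5)⁴ + (0.5)⁴ = 5/16 = 0.31.
- p = 0.75: P(X ≥ 3) = 4(0.75)³(0.25) + (0.75)⁴ = 0.422 + 0.316 = 0.738, so the criterion is missed with probability 0.26.
- Exact (Clopper-Pearson) 95% CI: 3 of 4 gives 19% to 99%. For 4 of 4 the lower limit is 0.025^(1/4) = 0.398, giving 40% to 100%.

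No possible result with 4 people has a lower limit at or above 75%.

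**3. H2b.** The text does not say whether 2 of 3 applies to each AoC or to their average, and the answer depends on it. Take a true attendance of 2/3 per meeting, with independence:
- One AoC attends at least 2 of 3 with probability 20/27 = 0.741. All four do so with probability 0.741⁴ = 0.30.
- The average is at least 2 if there are at least 8 of 12 attendances, with probability 0.63.

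**4. H2c.** The documents give no SD for the number of activities attended. I assume 2 to 3.5, n = 24 and independent participants.
- Half-width = t(0.975, 23) × SD/√24 = 2.069 × SD/4.899, which is 0.84 for SD 2 and 1.48 for SD 3.5.
- For the lower limit to reach 7, the observed mean must be about 7.84 (SD 2) to 8.48 (SD 3.5).
- Chance of an observed mean of at least 7 (normal approximation, SE = SD/√24):

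| True mean | SD 2 | SD 3.5 |
|---|---|---|
| 6.0 | 0.7% | 8% |
| 6.5 | 11% | 24% |
| 7.5 | 89% | 76% |
| 8.0 | 99.3% | 92% |

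At half an activity from the threshold the wrong side is observed 11% to 24% of the time; at a full activity, at most 8%.

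**5. Dependence.** Participants share group sessions within two cohorts, and the amendment text in Sections II and III places the second cohort in a different community. As an illustration only, an assumed intraclass correlation of 0.05 gives a design effect of 1 + 11 × 0.05 = 1.55, which widens the interval by √1.55 = 1.24.

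**The case against.** The plan can fairly be read as a descriptive pilot. It says so for Aim 2, gives that as the reason for having no power analysis, and in III.g warns that a small non-representative sample is likely to give inaccurate effect estimates and standard errors. On that reading only the verb is wrong. This largely stands, and it is why the point is minor.

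An interval also does little for H2a. As worded, H2a is a count among four named positions, not a sample from a population of AoCs, and no outcome could show 75%. This stands too: the interval can convey imprecision and nothing more.

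Two stronger readings are tempting, and the documents do not support them.

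- A reader might infer that the H2c mean conceals non-participation. If 17 attend all 10 activities and 7 attend none, the mean is 170/24 = 7.08 and the benchmark is met. But III.c.i.1 plans frequencies for the process outcomes, which would show the 7 zeros. That example also has an SD of about 4.6, outside the range assumed above.
- A reader might infer that feasibility will be declared or denied by chance. No section sets a go/no-go rule or rests feasibility on the thresholds alone. III.c describes a wider process evaluation with six process measures, usefulness and satisfaction data, and coded open-ended responses.

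What the objection does not answer is that two sections still announce a test that the analysis does not contain. III.g explains the absence of a power analysis, not the absence of intervals; III.f plans intervals for process measures in the same small sample.

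**Conclusion.** The point holds as a mismatch between wording and analysis. H2a to H2c are said to be tested, and the Aim 2 plan can only describe them. For H2a the imprecision is large and needs only the binomial model and independence between the AoCs. For H2b the criterion itself is ambiguous. For H2c the uncertainty is moderate: 0.8 to 1.5 activities either side of the mean under an assumed SD of 2 to 3.5 and independent participants, so it bears on the conclusion mainly when the mean is within about one activity of 7. Correlation within cohorts, or fewer than 24 analysed, could widen that. Severity is minor: Aim 2 is openly descriptive, and the change affects what may be concluded rather than how the study is run.

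**What to change.** - In I.b.ii and III.c, for H2a to H2c only, replace the statement that they will be tested by one that they are descriptive benchmarks, reported as met or not met.
- In III.c.i.1, report the H2c mean with a 95% CI, together with the number of participants attending at least 7 of 10 activities, taken from the frequencies already planned. Note that the interval assumes independent participants.
- Report H2a as a count out of 4. Show its exact CI only to convey imprecision, and make no claim about a wider acceptance rate.
- Report H2b for each AoC.
- State that a met H2c benchmark whose interval extends below 7 will not be reported as showing that participation exceeds 70%.

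This costs a few sentences and minutes of analysis on data already being collected, with no added burden for participants. The downside is a less favourable feasibility statement when the mean falls close to the threshold.
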